NAS is manifested by central nervous system irritability (high pitch and inconsolable crying, irritability and sleep disturbances), autonomic nervous system over-reactivity (sweating, yawning, sneezing), gastrointestinal manifestations (poor feeding, emesis and loose stools) and respiratory distress (tachypnea and nasal congestion) (Finnegan 1975; Finnegan, 1976; Kaltenbach, 1986; Desmond 1975). The standard of care is to treat these infants with a slow taper of opioid but to date there is no established gold standard for that taper (Cochrane, 2010). The lack of high-quality research in the treatment of NAS has led to wide variations in medications and protocols (Patrick, 2014; O'Grady, 2009; Sarkar, 2006) and data on changes in the utilization of NICU resources in the treatment of affected infants are lacking (Tolia, 2015).

For the time frame July 1, 2013 through September 30, 2014, 300 infants with NAS have been cared for at the Johns Hopkins All Children's Hospital (JHACH) NICU with an average length of stay of 30 days. The average length of stay has recently decreased to 22-25 days with implementation of strict management guidelines and protocols. Accounting for an average daily cost of \$2062.50, the burden translates into medical costs averaging \$48,468.75 per infant. With the proposed model involving methadone treatment, we anticipate at most 14 days of care in the NICU at a cost of \$28,875.00, followed by 10 days of home care at an anticipated cost of \$190/day for a total cost of \$30,775. This is an anticipated reduction in cost of \$17,693.75 per patient.

The prolonged stay has other social and medical impacts – including limitation in parental interaction and bonding, exposure to nosocomial infections, and taking up valuable resources both in terms of personnel and equipment. Once discharged home, these infants are often exposed to inconsistent caregiving, family instability, out of home placements, chronic stress, abuse, neglect and poverty – all of which affect their health and development, thus incurring even greater societal costs. To date, there are no published data on the in-home pharmacologic treatment of these infants.

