JHACH NICU Stork Nurses communicate with the Bayfront Baby Place Nurses a minimum of two times per day to check for potential NAS infants and transfers. Such communication readily identifies candidate mother / infant dyads shortly after delivery, and the pre-qualified mother will be approached for consent by a member of the study team (MD or mid-level).

b) **Comparison Group:** Mothers of infants who are admitted to the JHACH NICU with the diagnosis of NAS and who are started on treatment with a narcotic different than methadone, will be identified during the first week of NICU admission. Those mothers will be approached for consent by a member of the study team.

The difference between the two groups is further delineated in the tables below.

NOTE regarding screen failures:

Up to 35% of infants with NAS do not require pharmacological treatment as their symptomatology is controlled by non-pharmacological interventions. Such infants are released home after an observation period of about 7 days. If a patient was consented for either the comparison or methadone group and did not require pharmacological treatment for NAS, these infants will be considered screen failures. Accordingly, there will be no measures of bonding and depression, no outpatient follow-up by either KHC or the JHACH pediatrician and no assessment of development.

Principal Investigator: [name], MPH

Application Number: IRB00107690

Study Design:

Study Schedule of Events:

a) Methadone Treatment Group

Study Intervention	Enrollment	While inpatient	After discharge home on methadone	6 – 8 weeks of age	4 months of age	8 months of age	12 months of age
Informed Consent	X						
Methadone Administration		X ^a	X ^b				
Child Protective Investigator (CPI) clearance of the home		X (prior to discharge)					
Social Work Home Assessment			X (upon discharge)				
Face-to-face teleconferencing			X ^c				
Finnegan scoring		X	X ^b				
Kids Home Care Visit			X ^b		X ^f	X ^f	X ^f
JHACH Outpatient Pediatrician H&P, PE			X ^d				
The Postpartum Bonding Questionnaire (PBQ)		X ^e		X ^f			
Edinburgh Postnatal Depression Scale (EPDS)		X ^e		X ^f			
Ages And Stages Questionnaire (ASQ)					X	X	X

^a Per protocol

^b Twice daily until 48 hours after total weaning of medication is achieved

^c Every 3-4 hours until 48 hours after total weaning of medication is achieved

^d Within 1-2 days after discharge then weekly for 4 weeks until discontinuation of methadone treatment

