JHACH admitted and average of 131 NAS infants in recent years who required pharmacological treatment for NAS. Approximately 30% of those mother/infant dyads were residents of PAR. We anticipate to enroll 25 mother/baby dyads into the methadone treatment group and 25 mother/baby dyads into the control group for a total of 100 participants. Both the mother and infant are research participants. Those infant participants are defined as 1) needing methadone or other opiate treatment, 2) transitioning to home care, and 3) successfully weaning off medication.

This number has been extrapolated taken into account the following projections/assumptions: 1) not all mothers staying at PAR will meet criteria for participation, and 2) polydrug use may be discovered at the time of delivery thus excluding from participation, and 3) 20-40% of infants enrolled may need adjunct second line therapy.

b. Blinding, including justification for blinding or not blinding the trial, if applicable.

This is a demonstration study with no blinding of subjects involved.

c. Justification of why participants will not receive routine care or will have current therapy stopped.

All infants will continue to receive routine hospital care. Methadone treatment is approved by the FDA, and endorsed by the AAP for inpatient and outpatient treatment of infants with NAS. While methadone is not used as the standard of care at JHACH NICU for infants with NAS at birth, it is still used for later iatrogenic withdrawal in the NICU and other intensive care units in the hospital.

d. Justification for inclusion of a placebo or non-treatment group. N/A Will need to justify this as a comparison groups has been included

e. Definition of treatment failure or participant removal criteria.

As delineated above, infants will be off-treatment from the demonstration project if 1) they require the addition of a second-line of pharmacological treatment or 2) they require re-admission to the

Principal Investigator: [name], MPH

Application Number: IRB00107690

hospital. Data will still be collected until final hospital discharge for these infants and the maternal assessments of bonding and depression will remain ongoing. .

Other Indications for participant off-study:

- a. Parent withdraws informed consent at any time
 - b. Infant transfers to another hospital.
 - c. Infant experiences an unexpected adverse event deemed related to study intervention

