- a. **Primary outcome variable:** Length of Stay (LOS)

- b. **Additional outcomes of interest to be examined:**

- 1) Maternal bonding measured by the Postpartum Bonding Questionnaire (PBQ);
- 2) Depressive symptomatology measured by Edinburgh Postnatal Depression Scale (EPDS);
- 3) Hospital readmission within 30 days;
- 4) Weight gain of greater than 15% above Birth Weight at 30 days of age;
- 5) Age appropriate development as screened by the Ages and Stages questionnaires.

- c. **Statistical plan including sample size justification and interim data analysis:**

Demographic and clinical characteristics of participants will be summarized using means with standard deviations (SD) or median with interquartile ranges for continuous variables and counts and percentages for categorical variables. The primary outcome, length of stay, will be summarized using mean (SD) or median and interquartile range and will be compared to the comparison group using the t-test or Wilcoxon rank sum test as appropriate. For the secondary outcomes, the scores on the postpartum bonding questionnaire or the Edinburgh Postnatal Depression Scale will be summarized using means (SD) and compared to other patients in the comparison group using independent two-sample t-test. The proportion of participants that are readmitted within 30 days or with a weight gain of greater than 15% above birth weight will be compared to the comparison group using a Chi-squared or Fishers exact test as appropriate. Among the methadone cohort, we will calculate percentage of infants with age appropriate development at 4, 8 and 12 months. We anticipate that 25 mother-child dyads in each group will be available for the study. We expect that the mean LOS in the comparison group will be around 25 days (based on historical data). This sample size will allow us to estimate differences in LOS of >4 days with sufficient power (80%) at an alpha of 0.05, assuming a standard deviation of 5 days for both groups.

Early stopping rules:

Infant: requiring therapy with a second drug

Parents: desire to remove the infant from the study at any time or when infant is transferred to another hospital.

7. Risks

- a. **Medical risks, listing all procedures, their major and minor risks and expected frequency:**

Principal Investigator: [name], MPH

Application Number: IRB00107690

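### Comparison enrolment is not tied to methadone enrolment, so the comparison group can fill first and the two groups can differ in calendar time in a unit where LOS has already shifted.

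*Combined protocol and SAP*

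**What the plan says.** Eligibility and Enrollment Process, part b, says that mothers of NICU infants with NAS who start a different narcotic "will be identified during the first week of NICU admission. Those mothers will be approached for consent by a member of the study team". That week is counted from the infant's own admission. The Accrual paragraph adds a target: "We anticipate to enroll 25 mother/baby dyads into the methadone treatment group and 25 mother/baby dyads into the control group". General Design Issues calls the study a non-randomized prospective cohort. None of these places gives an enrolment ratio, pairing, a date window or a rule for when either group opens or closes.

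The two groups draw on different pools. The Accrual paragraph gives an average of 131 drug-treated NAS infants and states that "Approximately 30% of those mother/infant dyads were residents of PAR". Section 4 limits the methadone group to mothers under PAR's care who also meet conditions on county, programme compliance, stable dose, prescreening and child-protection status. It further excludes mothers whose drug screen at delivery shows drugs other than opiates. The comparison group has none of these conditions, apart from an exclusion for infants expected to enter state custody or be sheltered.

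Section 6c compares LOS between groups by a t-test or Wilcoxon rank sum test, with no term for calendar time. On unit history, Section 3 reports a mean LOS of 30 days for July 2013 to September 2014 and then states: "The average length of stay has recently decreased to 22-25 days with implementation of strict management guidelines and protocols".

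**The concern.** A concurrent comparison group is useful here because it can control for changes in NICU practice, which the historical average cannot. That holds only if both groups are enrolled over the same months. If comparison infants come mostly from the start of accrual and methadone infants from throughout it, any change in LOS over that time falls unequally on the groups, and the unadjusted test attributes it to methadone. If LOS keeps falling, the error favours methadone. The unit's LOS has already moved by more than the 4-day difference that the sample size targets.

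**Working it through.** **1. The plan's own figure.** Section 6c gives the target as "This sample size will allow us to estimate differences in LOS of >4 days", sets the error rates in the phrase "with sufficient power (80%) at an alpha of 0.05", and describes the spread as "assuming a standard deviation of 5 days for both groups". The two-sided normal formula gives n = 2 × 5² × (1.960 + 0.842)² / 4² = 24.5, so 25 per group. Power at 25 per group is 80.7% (normal) or 79.1% (noncentral t). The stated sample size reproduces and is not in question.

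**2. Pools.** Using 131 and 30% from the Accrual paragraph: 131 × 0.30 = 39.3 and 131 × 0.70 = 91.7, a ratio of 2.3 before the extra methadone-group criteria. The 30/70 split is approximate. The 30% counts PAR residents, while the criterion is being under PAR's care, and nothing bars PAR infants from the comparison group.

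**3. Enrolment after the comparison group reaches 25.** Suppose both groups open together, enrol at a steady rate and stop at 25. With equal uptake the share of methadone infants enrolled after the comparison group fills is 1 − 39.3/91.7 = 57%. This depends only on the 30/70 split, not on the uptake level or on whether 131 is an annual figure.

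**4. Gap in mean enrolment dates.** This needs 131 read as per year (an assumption; no time unit is given) and uptake figures (also assumed). Months to 25 = 12 × 25 / (pool × uptake). Gap = (methadone months − comparison months) / 2.

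| Uptake, comparison / methadone | Months to 25, comparison / methadone | Gap in mean dates (months) | Methadone infants enrolled after comparison fills |
|---|---|---|---|
| 40% / 40% | 8.2 / 19.1 | 5.5 | 57% |
| 50% / 30% | 6.5 / 25.4 | 9.5 | 74% |
| 25% / 50% | 13.1 / 15.3 | 1.1 | 14% |

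**5. Bias in LOS.** The past fall was 30 − 25 = 5 to 30 − 22 = 8 days. Bias = gap in years × drift per year.

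- No continuing drift: bias is 0, whatever the gap.
- Continuing drift of 1.25 to 4 days per year (assumed: 5 days over 4 years to 8 days over 2 years): 0.1 to 0.4 days for the 1.1-month gap, 0.6 to 1.8 days for 5.5 months, and 1.0 to 3.2 days for 9.5 months.

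**6. Effect on the test.** With no treatment effect, 25 per group and SD 5, the noncentral t gives these two-sided rejection rates: 5% for no shift, 6.8% for 0.57 days, 24% for 1.82 days and 59% for 3.15 days.

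**The case against.** The strongest objection is that continuing drift is not in the documents. Section 3 ties the fall in LOS to management guidelines introduced before this study, and the routine-care text says that escalation and weaning follow set protocols. If that change was a completed step, the bias is zero. This stands, and zero belongs in the range.

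A reader might infer that following the text necessarily fills and closes the comparison group early. The documents do not say so. They do not state that both groups open together, that every eligible comparison mother is approached, or that enrolment closes at 25. Early filling is possible and nothing prevents it; that is as far as the text goes.

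A reader might also take the 30% as a ceiling on the methadone pool. It counts PAR residents, whereas mothers under PAR's care may be a wider group, so the pool may be larger. Uptake could also favour the methadone group, whose mothers are contacted before delivery and whose families receive items at discharge home. The third row of the table shows how small the gap then becomes.

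Finally, the hypothesis is a fall from 25 days to under 15. A drift of about 3 days could not account for a difference of 10 days. That is correct, but the test is sized for 4 days, and a smaller observed difference would be hard to interpret.

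None of this supplies the missing link between the two enrolments.

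**Conclusion.** The gap is real: no provision keeps comparison and methadone enrolment in step, and the methadone pool is the smaller and more restricted one. The 57% figure rests on equal uptake, a 30/70 split and a simultaneous start. The date gap ranges from about 1 to 9.5 months under the uptake values shown.

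The bias in the LOS comparison ranges from zero to about 3 days. Its upper part requires LOS to keep falling by up to 4 days a year, which is an assumption. A reader might infer from the earlier 5-to-8-day fall that a bias of that order is expected; the documents do not support that. What the fall shows is that LOS in this unit responds to care guidelines by more than the trial's 4-day target. This is a design weakness worth correcting, not an error in the sample size.

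**What to change.** In Eligibility and Enrollment Process, part b, add that the number of comparison infants enrolled will never exceed the number of methadone infants counted toward the 25. The team approaches the next consecutive eligible infant started on another narcotic, moves on if consent is declined, and keeps comparison enrolment open until the last methadone infant is enrolled.

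In the Accrual paragraph, state whether 25 means infants started on treatment or completers, and apply the same rule to both groups. This matters because that paragraph describes participants as going to home care and weaning successfully, and expects 20–40% to need adjunct therapy. If those infants do not count, 25/0.8 = 31.3 to 25/0.6 = 41.7 methadone starts would be needed. A rule of one comparison infant per methadone start, capped at 25, would then still close the comparison group early.

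In Section 6c, report admission dates by group and add a sensitivity analysis of LOS adjusted for admission date. Adjustment alone is not enough, because it depends on extrapolation where the groups' dates do not overlap.

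The cost is a short amendment and a running count kept by the team. Comparison enrolment finishes later, alongside the methadone group. Pacing itself does not change the target of 25 per group; if 25 means completers, the additional starts follow from that definition. Pacing does not address other differences between PAR and non-PAR dyads.

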The rationale for amending that protocol relates to the reported premature initiation of Phenobarbital as adjunct therapy. Most protocols call for the initiation of adjunct therapy when first line medication fails (i.e. reaching maximal doses or requiring multiple re-escalations of dosing). In Table 1 however, phenobarbital initiation happens instead during the weaning process. Accordingly, a rather large number of infants get started and discharged home on phenobarbital (22.6%).

Our goal is to introduce second-line treatment when truly indicated (i.e. when maximal safe therapy fails) and to minimize discharge home on medication, as this approach, while minimizing the LOS, allows for infants to remain on medication for an indeterminate length of time.

Principal Investigator: [name], MPH

Application Number: IRB00107690

Demonstration Study Methadone Protocol

Initiation:

Initiate protocol for infants with 2 consecutive Finnegan scores > 8. Starting dose is 0.1 mg/kg/dose Q 6 hours (Table 2 - Step 1). As per hospital policy, medications may be given +/- 1 hour from scheduled administration time

Weaning:

Table 2. Initiation and weaning of methadone			
Step	Methadone Dose (mg/kg)	Interval	Minimum Number of Doses
Step 1	0.1	Q6 h	8
Step 2	0.07	Q12 h	2
Step 3	0.05	Q12 h	2
Step 4	0.04	Q12 h	2
Step 5	0.03	Q12 h	2
Step 6	0.02	Q12 h	2
Step 7	0.01	Q12 h	2
Step 8	0.01	Q24 h	1

Initial weaning: wean after 48 hours of stable scores (i.e. 2 consecutive 24 hour Finnegan score averages < 8)
Subsequent weaning: Wean to the next step if the 24 hour Finnegan score average is < 8;
If the 24-hour Finnegan score average is 8-10, do not wean;
If the 24-hour Finnegan score average is ≥ 11, follow escalation below.

Table 2 Escalation:

- Escalation will take place by going back one step in the dosing regimen (i.e. go from Step 5 to Step 4, etc.)
- If infant needs escalation from Step 2 to Step 1, one may consider either going back up the one step to Step 1 or giving an additional methadone dose.
- Weaning will resume after 24 hours of stable scores (i.e. a 24 hour average of <8)
- If infant fails Step 1 above, increase interval of dosing to Q 4 hour (Step 1A in table 3 below)

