If infant has 2 consecutive Finnegan scores that indicate severe withdrawal symptoms, despite non-pharmacological intervention, the PI or a co-Investigator needs to be informed. The PI or a co-investigator physician will assess each situation based on infant's medication dosage, its frequency and timing of administration, and one of the 3 following options will be offered: 1) re-escalate to the previous step; 2) consider giving an additional dose of methadone if > 4 hours before the next scheduled dose and 3) consider moving up the next scheduled dose without escalation.

Principal Investigator: [name], MPH

Application Number: IRB00107690

Weaning after Step 1 escalation (steps 1A through 1C)

Table 3. Methadone escalation after weaning failure			
Step	Methadone dose (mg/kg)	Interval	Minimum Number of doses
Step 1A	0.1	Q4 h	6
Step 1B	0.1	Q8 h	3
Step 1C	0.1	Q12 h	2

Weaning: Wean to the next step if the 24 hour Finnegan score average is < 8;
If the 24-hour Finnegan score average is 8-10, do not wean;
If the 24-hour Finnegan score average is ≥ 11, follow escalation below

Table 3 Escalation:

- If patient's dosing interval has to be escalated to table 3, weaning will follow as delineated in the table.
- If infant needs escalation from Step 1B to Step 1A, one may consider either going back up the one step to Step 1 or giving an additional methadone dose.
- Once infant weans to Step 1C, further wean will be to table 2, Step 2. Weaning will then follow the protocol for table 2.

Slight variation in timing of drug administration is inherent in the provision of medical care. JHACH policy allows for drugs to be administered by nursing staff within +/- 1-hour of the scheduled timing.

Differences between Table 1 and Table 2:

As mentioned above, this modified protocol allows for initiation and weaning indications that are more in line with the AAP recommendations and the JHACH culture of minimizing infant's discomfort and providing medication weaning in a safe and conservative fashion (Table 2).

The differences between tables 1 and 2 pertain to the following:

- 1) Finnegan scores that initiate treatment: 2 consecutive scores > 8 instead of 3 scores of ≥ 8
- 2) 24-hour Finnegan score averages to guide weaning, observation and re-escalation:
 - wean if the average is <8
 - observe if average 8-10, instead of 8-12
 - re-escalate for average ≥ 11 instead of ≥ 12

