- 3) Observe a 48-hour (instead of 24) of stable scores prior to initial weaning and prior to wean after re-escalation if patient falls in table 2.

C. Discharge home:

Infants will be discharged home or to Operation PAR when they are deemed stable by the treating team.

Principal Investigator: [name], MPH

Application Number: IRB00107690

Stability is defined as:

- 1) A maximal dose of methadone of ≤ 0.04 mg/kg at the time of discharge (Step 4 of Table 2), and
- 2) A history of successful weaning of methadone for a least 3 days prior to discharge, and
- 3) No dose re-escalation in the previous 72 hours prior to discharge.

Timing of medication administration may be changed gradually prior to discharge, as allowed by hospital policy, to accommodate outpatient administration by Kids Home Care.

Weaning at home will follow the weaning protocol delineated above. Finnegan scoring will be continued at home. It will be done twice daily by the visiting Kids Home Care RN. Virtual Finnegan scoring assessment will be done as described above every 3 to 4 hours by teleconferencing with the Kids Home Care RN versed in the care of infants with NAS.

D. Discontinuation of methadone:

Methadone will be discontinued when the dose is 0.01 mg/kg/dose every 24 hours and the previous 24-hour average if ≤ 6 .

E. Home observation post discontinuation of methadone:

Observe infant for 72 hours off medication with twice daily nursing visits. Treatment is considered successful if infant's 24-hour average remains < 8 .

This observation period is important as it allows to watch for possible rebound of symptomatology after cessation of medical intervention, and is in accordance with the standard of care that infants with NAS receive at JHACH. If during this observation period infants develop rebound symptomatology (defined as a 24 hour Finnegan score average of > 8), the nurse will institute appropriate measures of comforting infant and reducing / eliminating noxious stimuli. If comfort measures fail and Finnegan scores remain > 8 on 2 consecutive assessments performed at 3-4 hour intervals, methadone will be resumed at the last dose that infant received prior to discontinuation. Further Re-escalation and weaning will be performed per initial protocol.

F. Pediatrician Follow-up:

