It is standard of care for infants discharged from the JHACH NICU to see their primary care provider (PCP) within a day or two of discharge. Follow-up will be provided by an IRB approved study team JHACH Pediatrician, and will take place within one or two days after discharge then weekly for 4 weeks after discontinuation of methadone treatment.

G. Off-treatment Criteria:

Principal Investigator: [name], MPH

Application Number: IRB00107690

Off-treatment is defined as an infant who no longer qualifies for discharge home on methadone – i.e. requiring adjuvant pharmacological therapy or re-admission to the hospital while still on methadone

1. Addition of adjuvant therapy:

It is common for infants suffering from NAS to require the addition of an adjunct therapeutic agent for control of symptoms. This second-line agent varies among institutions but consists often of phenobarbital.

If demonstration project participants have uncontrolled NAS symptoms (defined as a 24-hour Finnegan score average ≥ 11 despite comfort measures and maximal methadone dosing – i.e. 0.1 mg/kg given every 4 hours), the infant will be placed on phenobarbital, the standard of care at JHACH NICU. Such infant will be off-treatment from the study i.e. will not qualify for subsequent discharge home prior to discontinuation of methadone. Maternal assessments of bonding and depression will remain ongoing. There will be no home nursing visits.

2. Re-admission to the JHACH NICU:

It is common for infants suffering from NAS not to tolerate weaning off medication. Re-escalation during that phase is common. If during the weaning phase, infant's Finnegan scores are > 8 on 2 consecutive scores despite comfort measures, the dose of methadone will be increased to the previous dose at which the patient's symptoms were well controlled.

If an infant requires consecutive re-escalation of medication with no control of symptoms (i.e. 24 hour Finnegan scores > 6), such infant will be re-admitted to the hospital.

- for infants who were discharged home on a dose of methadone that is < 0.04 mg/kg, such infant will be re-admitted to the hospital if consecutive re-escalation of methadone are required and infant reaches a dose of 0.05 mg/kg.

- for infants discharged home at a dose of 0.04 mg/kg, who do not tolerate weaning at home and who require dose escalation, the dose will be increased in 2 increments per protocol to a value of 0.07 mg/kg before re-admission to the hospital.

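### The Table 3 escalation rule is conditioned on a move from Step 1B to Step 1A but names Step 1 as the target: a minor internal inconsistency in an operative dosing rule

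*Combined protocol and SAP*

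**What the plan says.** All references are to the combined protocol and SAP, Study Procedures, unless stated otherwise.

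- **Table 2 (B. Methadone treatment).** Treatment starts at Step 1, 0.1 mg/kg every 6 h. Under Table 2 Escalation the general rule is "Escalation will take place by going back one step in the dosing regimen". A specific bullet covers the top of the table: "If infant needs escalation from Step 2 to Step 1, one may consider either going back up the one step to Step 1", or an additional dose. Failure of Step 1 leads into Table 3: "If infant fails Step 1 above, increase interval of dosing to Q 4 hour (Step 1A in table 3 below".
- **Table 3.** Three steps, all at 0.1 mg/kg: 1A every 4 h, 1B every 8 h, 1C every 12 h. Step 1 is not a row of this table. Under Table 3 Escalation: "If infant needs escalation from Step 1B to Step 1A, one may consider either going back up the one step to Step 1", again with an additional dose as the alternative.
- **Severe scores.** For two consecutive scores showing severe withdrawal, the PI or a co-investigator is informed and a physician chooses among three options, one of which is "re-escalate to the previous step".
- **G. Off-treatment Criteria, item 1.** Phenobarbital is added, and the infant goes off-treatment, if the 24-hour average is 11 or more at maximal methadone dosing, defined as "0.1 mg/kg given every 4 hours". That is Step 1A.
- **C. Discharge home.** Stability requires "A maximal dose of methadone of ≤ 0.04 mg/kg at the time of discharge".

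**The concern.** The Table 3 bullet disagrees with itself: its condition and its target name different regimens. This is a drafting inconsistency and not a dispute with the dosing design.

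It matters because the bullet is a live opioid dosing instruction for newborns. In Table 3 escalation is called for at a 24-hour Finnegan average of 11 or more. Followed literally, the bullet returns the infant to the regimen that had to fail before Table 3 was entered, at a lower daily dose than the condition implies. Step 1A is also the maximum that defines the phenobarbital and off-treatment rule, so the step names around it should be unambiguous.

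**Working it through.** The plan gives no daily-dose figure to reproduce. The check has two parts.

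**1. Daily dose under each reading.** The inputs are the per-dose amounts and intervals in Tables 2 and 3. Daily dose = mg/kg per dose × 24 / interval in hours.

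| Step | Calculation | mg/kg/day | Change from 1B |
|---|---|---|---|
| 1B (where the infant is) | 0.1 × 24/8 | 0.3 | – |
| 1 (target as written) | 0.1 × 24/6 | 0.4 | 0.4/0.3 − 1 = +33% |
| 1A (step named in the condition) | 0.1 × 24/4 | 0.6 | 0.6/0.3 − 1 = +100% |

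The target as written is 0.4/0.6 = 67% of the Step 1A daily dose, a gap of 0.6 − 0.4 = 0.2 mg/kg/day. As an illustration, take an infant at the 2.5 kg birth-weight minimum and assume dosing on that weight. Step 1B gives 0.3 × 2.5 = 0.75 mg/day, Step 1 gives 0.4 × 2.5 = 1.0 mg/day, and Step 1A gives 0.6 × 2.5 = 1.5 mg/day.

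**2. Which step the text supports.**

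- *Main evidence.* The condition itself says the move is to Step 1A. The target phrase speaks of one step up, and in Table 3 the row directly above 1B is 1A.
- *Support.* The back-one-step rule gives 1A for an infant on 1B, but it sits under Table 2 Escalation with a Table 2 example. The previous-step option also gives 1A, but its trigger differs (two consecutive severe scores) and it is one of three options.
- *Likely origin (an inference).* The Table 2 bullet has the same form, and there condition and target agree: Step 2 to Step 1, target Step 1. If it was carried over to Table 3 with only the condition updated, the present sentence results.

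**The case against.** The strongest reply is that the sentence largely corrects itself. It names Step 1A before it names Step 1, it speaks of a single step, and a clinician would have to leave Table 3 to act on the literal target. The heading above Table 3 treats 1A to 1C together as Step 1 escalation, so the word could be loose shorthand. The wording is permissive and an additional dose is also allowed.

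There are also safeguards:

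- An infant placed on Step 1 who fails it is sent to Step 1A by the Table 2 rule.
- Phenobarbital still requires failure at every-4-hour dosing.
- Severe scores bring in a physician investigator.
- Table 3 dosing is inpatient. Discharge requires 0.04 mg/kg or less, and under G.2 escalation at home reaches at most 0.07 mg/kg before re-admission, below the 0.1 mg/kg of Table 3. Section 7.b provides NICU monitoring during escalation.

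All of this stands, and it is why the point is minor. It does not remove the mismatch. No other text corrects the sentence, and shorthand for the whole of 1A to 1C would not say which interval to give.

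It can also be argued that every 6 h was meant as an intermediate between every 8 h and every 4 h. The documents do not exclude this, but the condition would then be wrong, so the sentence needs editing either way.

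**Conclusion.** The inconsistency is real, current and operative, and it is minor. If the target is followed literally, the infant receives 0.4 instead of 0.6 mg/kg/day, still above the 0.3 mg/kg/day of Step 1B. Confidence is high that condition and target disagree. That Step 1A was meant is the better-supported reading but needs clinical confirmation.

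The dose gap arises only for an infant who fails Step 1, reaches 1A, weans to 1B and relapses, and only if the clinician follows the target rather than the condition. The documents give no count of such infants. Among the 25 planned for the methadone group there may be few or none.

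Three stronger readings are tempting, and the documents do not support them:

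- *That G.2 settles the target as Step 1A.* It says "the dose of methadone will be increased to the previous dose at which the patient's symptoms were well controlled", and weaning from 1A requires a 24-hour average below 8. But 1A and 1B share the same 0.1 mg/kg dose and differ only in interval, and the values G.2 goes on to use are per-dose amounts. The passage also concerns re-admission. It does not decide the point.
- *That the literal reading leads to premature phenobarbital or off-treatment status.* It does not by itself, because that rule requires failure at every-4-hour dosing.
- *That length of stay, power or the analysis is affected.* Nothing in the documents quantifies a delay, and the sample-size assumptions do not depend on this sentence.

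**What to change.** Subject to confirmation by the clinical investigators, change the target in the Table 3 Escalation bullet from Step 1 to Step 1A and leave the rest of the sentence, including the additional-dose alternative, as it is. If the clinicians did intend Step 1, correct the condition instead so that it and the target name the same step.

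The cost is a wording amendment to one sentence. Sample size, visits, data collection and analysis do not change.
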